3.4. Duration of Treatment

Subjects may continue receiving GS-5829 once daily until disease progression (clinical or radiographic), unacceptable toxicity, withdrawal of consent or death, whichever comes first. See Section 3.5 for criteria for study drug discontinuation.

3.5. Criteria for Discontinuation of Study Drug

Study medication may be discontinued in the following instances:

- Documented progression of malignant disease
- Death
- Investigator discretion
- Non-compliance with study drug
- Important protocol deviation
- Pregnancy
- Subject decision
- Lost to follow-up
- Study termination by the sponsor
- Adverse Event

3.6. Criteria for Removal from Study

Subjects may be removed from the study for the following reasons:

- Documented progression of malignant disease
- Death
- Investigator discretion
- Withdrawal of consent
- Lost to follow-up
- Important protocol deviation
- Pregnancy
- Study termination by the sponsor

4. SUBJECT POPULATION

4.1. Number of Subjects and Subject Selection

Up to 30 subjects who meet the eligibility criteria will be enrolled in the Phase 1b Dose Escalation portion of the study.

Up to 120 subjects who meet the eligibility criteria will be enrolled in the Randomized Phase 2 Dose Expansion portion of the study.

4.2. Inclusion Criteria

Subjects must meet all of the following inclusion criteria to be eligible for participation in this study:

- 1) ≥ 18 years of age, female
- 2) Histologically or cytologically confirmed breast cancer with evidence of metastatic or locally advanced disease not amenable to resection or radiation therapy with curative intent and who have progressed during treatment with at least one prior hormonal therapy
 - a) Phase 1b Dose Escalation - Subjects may have had unlimited prior hormonal therapy and a total of 2 prior chemotherapy regimens (adjuvant chemotherapy is considered 1 regimen). Subjects may have progressed on fulvestrant or exemestane
 - b) Randomized Phase 2 Dose Expansion - Subjects may have disease progression during treatment or within 12 month of completion of endocrine therapy (tamoxifen, and/or AI) in the adjuvant setting, or disease progression during treatment with endocrine therapy (tamoxifen, AI or CDK4/6 inhibitor plus AI) for advanced/metastatic disease. Subjects may have had unlimited prior hormonal therapy, but must be naïve to fulvestrant in the metastatic setting. A total of 2 prior chemotherapies are allowed, however, only one for metastatic disease is permitted.
- 3) Documentation of ER positive breast cancer ($\geq 1\%$ positive stained cells by local standards) based on the most recent tumor biopsy, unless bone-only disease
- 4) Documented HER2-negative tumor based on local testing on most recent tumor biopsy (immunohistochemistry score 0/1+ or negative by in situ hybridization HER2/CP17 ratio < 2 or for single probe assessment HER2 copy number < 4)

- 5) Post, pre or peri-menopausal subjects considered to be in the post-menopausal state as defined by one of the following:
 - a) Age \geq 60 years
 - b) Age $<$ 60 years and cessation of regular menses for at least 12 consecutive months in the absence of chemotherapy, tamoxifen, toremifene, or ovarian suppression and serum estradiol and follicle-stimulating hormone (FSH) level within the post-menopausal range
 - c) Prior bilateral oophorectomy
 - d) Pre-/peri-menopausal women can be enrolled if amenable to be treated with the luteinizing-hormone releasing hormone (LHRH) agonist goserelin. Subjects must have commenced treatment with goserelin or an alternative LHRH agonist at least 4 weeks prior to C1D1. If subjects have received an alternative LHRH agonist prior to study entry, they must switch to goserelin on or before C1D1 for the duration of the study
- 6) Measurable disease defined per RECIST v. 1.1 or bone-only disease must have a lytic or mixed lytic blastic lesion that can be accurately assessed by CT or MRI. Subjects with bone-only disease and blastic-only metastases are not eligible
- 7) All acute toxic effects of any prior antitumor therapy resolved to Grade \leq 1 before the start of study drug dosing (with the exception of alopecia [Grade 1 or 2 permitted] and neurotoxicity [Grade 1 or 2 permitted])
- 8) Eastern Cooperative Oncology Group (ECOG) Performance Status of \leq 1
- 9) Life expectancy of \geq 3 months, in the opinion of the investigator
- 10) Adequate organ function defined as follows:
 - a) Hematologic: Platelets \geq 100 \times 10^9 /L; Hemoglobin \geq 9.0 g/dL; ANC \geq 1.5 \times 10^9 /L (without platelet transfusion or any granulocytic growth factors within previous 7 days of the hematologic laboratory values obtained at screening visit)
 - b) Hepatic: AST / ALT \leq 2.5 \times upper limit of normal (ULN) (if liver metastases are present, \leq 5 \times ULN); total or conjugated bilirubin \leq 1.5 \times ULN
 - c) Renal: Serum Creatinine \leq 1.5 \times ULN or creatinine clearance (CrCl) \geq 60 mL/min as calculated by the Cockroft-Gault method
- 11) Coagulation: International Normalized Ratio (INR) \leq 1.2
- 12) Negative serum pregnancy test ([Appendix 5](#))
- 13) Female subjects of childbearing potential who engage in heterosexual intercourse must agree to use protocol specified method(s) of contraception as described in [Appendix 5](#)

- 14) Females who are nursing must agree to discontinue nursing before C1D1
- 15) Able and willing to provide written informed consent to participate in the study

4.3. Exclusion Criteria

Subjects who meet *any* of the following exclusion criteria are not to be enrolled in this study:

- 1) History or evidence of clinically significant disorder, condition, or disease that, in the opinion of the investigator or the Gilead medical monitor would pose a risk to subject safety or interfere with the study evaluations, procedures, or completion
- 2) Known brain metastasis or leptomeningeal disease. Note: if treated and stable at least 6 months prior to enrollment, subject is eligible.
- 3) Uncontrolled intercurrent illness including, but not limited to, active uncontrolled infection, active or chronic bleeding event within 28 days prior to C1D1, uncontrolled cardiac arrhythmia, or psychiatric illness/social situation that would limit compliance with study requirements as judged by treating physician
- 4) Myocardial infarction, symptomatic congestive heart failure (New York Heart Association Classification > Class II), unstable angina, or serious uncontrolled cardiac arrhythmia within 6 months of C1D1
- 5) Major surgery, defined as any surgical procedure that involves general anesthesia and a significant incision (i.e., larger than what is required for placement of central venous access, percutaneous feeding tube) within 28 days of C1D1
- 6) Impairment of gastrointestinal (GI) function or GI disease that may significantly alter the absorption of GS-5829, including any unresolved nausea, vomiting, or diarrhea that is CTCAE Grade > 1
- 7) Minor surgical procedure(s) within 7 days of enrollment or randomization, or not yet recovered from prior surgery (placement of central venous access device, fine needle aspiration, or endoscopic biliary stent \geq 1 day before enrollment or randomization is acceptable)
- 8) History of a concurrent or second malignancy, except for: adequately treated local basal cell or squamous cell carcinoma of the skin; cervical carcinoma in situ; superficial bladder cancer; adequately treated Stage 1 or 2 cancer currently in complete remission; any other cancer that has been in complete remission for \geq 5 years

- 9) Anti-tumor therapy (chemotherapy, chemoradiation, radiation, antibody therapy, molecular targeted therapy) within 21 days or 5 half-lives whichever is longer, of C1D1 (6 weeks for nitrosoureas, mitomycin C, or molecular agents with $t_{1/2} > 10$ days); 5 half-lives of any investigational drug. Concurrent use of goserelin for pre-/peri-menopausal breast cancer and exemestane or fulvestrant per the protocol are permitted
- 10) History of long QT syndrome or whose corrected QT interval (QTc) measured (Fridericia method) at screening is prolonged (> 470 ms). Subjects who screen fail due to this criterion are not eligible to be re-screened
- 11) Prior exposure to any bromodomain (BET) inhibitors
- 12) Known hypersensitivity to the study drugs (GS-5829, fulvestrant or exemestane), the metabolites, or formulation excipients
- 13) Immunotherapy within 6 months of C1D1
- 14) Evidence of bleeding diathesis or clinically significant bleeding, within 28 days of C1D1 or history of hemoptysis of ≥ 2.5 mL/1 teaspoon within 6 months of C1D1
- 15) Anticoagulation/antiplatelet therapy within 7 days of C1D1, including acetylsalicylic acid, low molecular weight heparin, or warfarin
- 16) Known human immunodeficiency virus (HIV) infection
- 17) Hepatitis B surface Antigen (HBsAg) positive
- 18) Hepatitis C virus (HCV) antibody positive with HCV RNA positive
- 19) Use of moderate/strong cytochrome P450 (CYP) 3A4 inhibitors or moderate/strong CYP3A4 inducers within 2 weeks prior to C1D1
- 20) History of high grade esophageal or gastric varices

5. INVESTIGATIONAL MEDICINAL PRODUCTS

5.1. Enrollment

This is an open-label study. All baseline tests and procedures must be completed prior to the administration of the first dose of study drug on Day 1. It is the responsibility of the investigator to ensure that subjects are eligible for the study prior to enrollment.

Up to 30 subjects will be enrolled in the Phase 1b Dose Escalation portion of the study, each subject will be assigned to either Group A (exemestane +GS-5829) or B (fulvestrant + GS-5829) based on prior treatment. Enrollment in Group A will be stopped after completion of the 4 mg GS-5829 dose level safety assessments. Subjects who were previously enrolled/treated in Group A will continue to be followed and managed according to the protocol as outlined below.

Approximately 120 female subjects who are post-menopausal with ER+/HER2- BrCa and who have had disease progression following endocrine therapy will be randomized in a 2:1 ratio to receive fulvestrant + GS-5829 or fulvestrant alone. Randomization will be stratified by prior CDK4/6 inhibitor status plus AI (naïve vs. progressed). The target number of subjects in each of the 2 strata will be approximately 60 (40 for GS-5829 in combination with fulvestrant and 20 for fulvestrant alone).

A subject will be considered enrolled once they have been registered in the Interactive Web Response System (IxRS).

5.2. Description and Handling of GS-5829

5.2.1. Formulation

GS-5829 will be supplied as round, plain-faced tablets containing 1 mg or 5 mg. The 1 mg tablet is film-coated gray and the 5 mg tablet is film-coated orange.

In addition to the active ingredient, 1 mg tablets contain the following commonly used excipients: microcrystalline cellulose, lactose monohydrate, crospovidone, magnesium stearate, polyvinyl alcohol, titanium dioxide, polyethylene glycol, talc, and iron oxide black.

In addition to the active ingredient, 5 mg GS-5829 tablets contain the following commonly used excipients: microcrystalline cellulose, lactose monohydrate, crospovidone, magnesium stearate, polyvinyl alcohol, titanium dioxide, polyethylene glycol, talc, FD&C yellow #6, and iron oxide yellow.

5.2.2. Packaging and Labeling

GS-5829 tablets are provided in white, high density polyethylene bottles with desiccant and polyester packing material. Each bottle contains 30 tablets and is enclosed with a white, continuous thread, child-resistant screw cap with an induction-activated, aluminum-faced liner.

Study drug(s) to be distributed to centers in the US and other participating countries shall be labeled to meet applicable requirements of the United States Food and Drug Administration (FDA), EU Guideline to Good Manufacturing Practice – Annex 13 (Investigational Medicinal Products), and/or other local regulations.

5.2.3. Storage and Handling

GS-5829 tablets should be stored at controlled room temperature until required for administration. Controlled room temperature is defined as 25°C (77°F); excursions are permitted between 15°C and 30°C (59°F and 86°F). Storage conditions are specified on the label.

Until dispensed to the subjects, all bottles of study drug should be stored in a securely locked area, accessible only to authorized site personnel. To ensure the stability and proper identification, the drug product should not be stored in a container other than the container in which it was supplied. Consideration should be given to handling, preparation, and disposal through measures that minimize drug contact with the body. Appropriate precautions should be followed to avoid direct eye contact or exposure when handling GS-5829 tablets.

Commercially available product of exemestane and fulvestrant will be used for the study. Further information regarding formulation is available in the Prescribing Information for commercial products.

5.3. Dosage and Administration of GS-5829, Exemestane and Fulvestrant

GS-5829 tablets will be provided by Gilead Sciences, Inc. and will be taken orally. Initiation of treatment with the study drug will take place after enrollment and cohort assignment. Subjects will take their dose of study drug at approximately 24-hour intervals. Tablets should be taken whole, they should not be chewed or crushed. To reduce inter-subject variability on efficacy and safety, subjects will be instructed to take GS-5829 approximately 1 hour before or 2 hours after a meal. Grapefruit juice is prohibited while on study drug.

GS-5829 tablets will be self-administered orally once daily, beginning on C1D1 of the study and thereafter at approximately the same time each day until EOT.

For subjects in Group A (Phase 1b), exemestane 25 mg tablets will be self-administered orally once daily (or in accordance with locally approved labelling), beginning on C1D1 of the study and thereafter at approximately the same time each day until the EOT. Exemestane will be dispensed to subjects at visits on the first day of each cycle.

For subjects in Group B (Phase 1b) and in the Phase 2 Dose Expansion, fulvestrant will be administered intramuscularly (in accordance with locally approved labeling) by the clinic staff approximately every 28 days (\pm 3 days) until the EOT.

For subjects in the Randomized Phase 2 Dose Expansion phase and for subjects in Group B of the Phase 1b Dose Escalation whom are treatment naïve (in metastatic setting) and for all

subjects for whom C1D1 is the subject's first dose of fulvestrant, a one-time additional dose of 500 mg fulvestrant will be administered on C1D15 (\pm 3 days).

5.3.1. Dose Adjustment of GS-5829

If at any time in the study, a subject experiences a toxicity consistent with a Grade 4 AE that is deemed to be related to GS-5829, GS-5829 treatment will be discontinued permanently, with the exception of Grade 4 neutropenia, thrombocytopenia, or alopecia. If a subject experiences non-hematologic Grade 3 toxicity consistent with a DLT (See Section 3.2), dosing with GS-5829 will be postponed until the toxicity is resolved to Grade 0 or 1 (as defined by the CTCAE, version 4.03) or returns to the subject's baseline value. If the toxicity resolves to Grade 0 or 1 or returns to the subject's baseline value within 28 days from the start of the event, the subject may resume dosing of GS-5829 at a dose that is at least one dose level lower after discussion with the Gilead medical monitor (See Table 5-1). If a subject has Grade 4 neutropenia, Grade 3 neutropenia with fever, or Grade 3 thrombocytopenia, GS-5829 should be interrupted for up to 28 days and/or until the toxicity resolves to \leq Grade 1. If the Grade 4 neutropenia or Grade 3 fever and neutropenia resolves within 4 days (7 days for Grade 3 thrombocytopenia), then the subject may resume dosing at the same dose. If the Grade 4 neutropenia or Grade 3 fever and neutropenia takes $>$ 4 days ($>$ 7 days for Grade 3 thrombocytopenia), but within 28 days to recover, then the dose of GS-5829 must be resumed at a lower dose. If the Grade 4 neutropenia, Grade 3 fever and neutropenia or Grade 3 or higher thrombocytopenia takes longer than 28 days to recover then GS-5829 must be permanently discontinued. Grade 4 thrombocytopenia observed at any time must be followed by a dose reduction.

If the recurrent toxicity is hematologic a second dose decrease is allowed (lowest dose allowed is 2 mg) in either total daily dose or by a change in schedule such that the total amount of GS-5829 administered over a 28 day period is decreased by at least 25%.

Table 5-1. Dose Reduction of GS-5829

HEMATOLOGICAL ADVERSE EVENTS	
Neutropenia	
Grade \leq 3 Neutropenia	Maintain current dose level and schedule.
Grade 4 neutropenia (or occurrence of Grade \geq 3 neutropenia (ANC $<$ 1000/mm 3) with fever (a single temperature of $>$ 38.3°C or a sustained temperature of \geq 38°C for more than one hour) or infection	Hold dosing with GS-5829 until the toxicity is resolved to \leq Grade 1. If the toxicity resolves to \leq Grade 1 within 4 days, the subject may resume dosing of GS-5829 at the same dose. If recovery to Grade \leq 1 takes $>$ 4 days, but within 28 days, then the subject may resume dosing of GS-5829 at a dose that is at least one dose level lower after discussion with the Gilead medical monitor. Granulocyte colony-stimulating factor (GCSF) is allowed (but not concurrent with GS-5829)

HEMATOLOGICAL ADVERSE EVENTS

Thrombocytopenia

Grade \leq 2 Thrombocytopenia	Maintain current dose level and schedule.
Grade 3 Thrombocytopenia	Hold dosing with GS-5829 until the toxicity is resolved to \leq Grade 1. If the toxicity resolves within 7 days, the subject may either resume at the same dose or a dose with is one level lower or at an intermittent dosing schedule (at least 25% less GS-5829 in a 28 day dosing period) after discussion with the Gilead medical monitor. If the thrombocytopenia takes 7-28 days to recover then the subject must resume at a dose one level lower or at an intermittent dosing schedule after discussion with the Gilead medical monitor.
Grade 4 Thrombocytopenia	Hold dosing with GS-5829 until the toxicity is resolved to \leq Grade 1. If the toxicity resolves within 28 days, the subject may either resume at a dose with is at least one level lower, or at intermittent dosing schedule (at least 25% less GS-5829 in a 28 day dosing period) after discussion with the Gilead medical monitor.

NON-HEMATOLOGICAL ADVERSE EVENTS

Hepatic Adverse Events (elevations in ALT or AST and/or bilirubin)

Grade 1 (ALT/AST \leq 3 x ULN) (Bilirubin \leq 1.5 x ULN)	Maintain current dose level and schedule.
Grade 2 (ALT/AST $>$ 3-5 x ULN) (Bilirubin $>$ 1.5 - \leq 3 x ULN)	Maintain current dose level and schedule. Monitor ALT, AST, ALP, and bilirubin at least once a week.
Grade 3	Hold dosing until \leq Grade 2. Permanently discontinue if any Grade 3 or Grade 4 elevation in AST or ALT associated with a Grade 2 elevation in bilirubin
Grade 4	Permanently discontinue GS-5829

Non-Hepatic, Non-Hematologic Adverse Events

Grade \leq 2	No change in dosing required. Dosing may be interrupted until Grade \leq 1 or baseline
Grade 3	Hold dosing until \leq Grade 1 and decrease dose by at least one dose level lower or at intermittent dosing schedule (at least 25% less GS-5829 in a 28 day dosing period) after discussion with the Gilead medical monitor.
Grade 4	Permanently discontinue GS-5829

For subjects only enrolled to Phase 2 part of the study: if a subject tolerates a reduced dose for $>$ 4 weeks, GS-5829 dose may be increased to the next higher dose level, at the discretion of the investigator and after discussion with Gilead medical monitor. Successive adjustments to progressively higher dose levels can be made at 4-weeks intervals up to the starting dose level.

If the toxicity does not resolve or return to baseline, or subject experiences a recurrence of the toxicity after restarting study drug at a lower dose or if the toxicity does not resolve within 28 days, study drug(s) GS-5829, exemestane (Group A Phase 1b) or fulvestrant will be permanently discontinued and the subject will return for an EOT and a 30-day Safety Follow-Up visit. If a subject who is randomized to the combination arm discontinues one study drug for any reason, such as toxicity the other study drug will be discontinued as well.

If the subject was not receiving GS-5829 at the time disease progression was documented (e.g., due to reversible toxicity), after discussion with the Gilead medical monitor, GS-5829 may be re-started if the criteria for resuming treatment are met and the investigator feels it is in the subject's best interest to do so.

If a subject develops a recurrence of the same Grade 3 or 4 hematologic or any non-hematologic toxicity that the investigator considers related to GS-5829 and is clinically significant at the lower dose, then the subject should be permanently discontinued from all study drug(s).

After the 28 day DLT period in the Phase 1b Dose Escalation and at any time in the Randomized Phase 2 Dose Expansion, in the event of a Grade 2 hematologic or non-hematologic toxicity the investigator considers related to GS-5829, GS-5829 may be interrupted per the investigator's discretion for a maximum of 28 days and resumed at either the same or a lower dose.

Subjects whose dose of exemestane (Group A Phase 1b) or fulvestrant is interrupted for a non-drug related toxicity for up to 28 days, or whose dose of GS-5829 is interrupted for up to 28 days, and are deemed by the investigator to be clinically benefiting from the combination treatment prior to dose interruption, may resume combination treatment.

Non-drug related dose interruptions for longer than 15 or 28 days (exemestane or fulvestrant respectively), or longer than 28 days for GS-5829 in subjects who do not have disease progression may be considered for resumption of study drugs after discussion with the Gilead medical monitor.

No dose reduction of GS-5829 below 3 mg is allowed.

Table 5-2. Dose Reduction of GS-5829

Dose at time of toxicity (mg)	Restarting dose level (mg)
9	6
6	4
4*	3**
3	2

* Dose level 1

** Dose level -1

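### For an isolated Grade 3 liver-test rise judged consistent with a DLT, the text of protocol Section 5.3.1 and the hepatic row of Table 5-1 set different restart thresholds, and nothing says which governs

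*Protocol*

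**What the plan says.** **Text of protocol Section 5.3.1.** When a subject has a non-hematologic Grade 3 toxicity consistent with a DLT, "dosing with GS-5829 will be postponed until the toxicity is resolved to Grade 0 or 1" or has returned to the subject's baseline. If that happens within 28 days of onset, the subject "may resume dosing of GS-5829 at a dose that is at least one dose level lower", after discussion with the medical monitor. The sentence ends with a pointer to Table 5-1. It makes no exception for liver tests.

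**Table 5-1, hepatic block (ALT or AST and/or bilirubin).**
- Grade 2: "Maintain current dose level and schedule. Monitor ALT, AST, ALP, and bilirubin at least once a week".
- Grade 3: "Hold dosing until \leq Grade 2", followed by the stopping clause "Permanently discontinue if any Grade 3 or Grade 4 elevation in AST or ALT associated with a Grade 2 elevation in bilirubin". No restart dose or schedule is given.

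**Table 5-1, non-hepatic non-hematologic block, Grade 3.** "Hold dosing until \leq Grade 1 and decrease dose by at least one dose level lower or at intermittent dosing schedule".

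**Further down Section 5.3.1.** A general stop applies: "if the toxicity does not resolve within 28 days, study drug(s) GS-5829, exemestane (Group A Phase 1b) or fulvestrant will be permanently discontinued".

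**The concern.** Two written safety rules cover one event and give opposite answers. Take a subject whose Grade 3 ALT has come down to Grade 2. The text keeps GS-5829 on hold; the hepatic row ends the hold. A subject who plateaus at Grade 2 never meets the text's restart condition but already meets the table's.

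Re-exposure after a liver DLT would then depend on which part of the section a site reads. It would also be unclear whether a restart at Grade 2 followed the protocol, although SAP Section 4.3 plans a summary of important protocol deviations.

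**Working it through.** No sample-size or power figure is involved, so the check sets the provisions side by side.

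**Step 1. Does the text rule reach liver tests?** Yes, for some events. The DLT definition in protocol Section 3.2 includes Grade 3 or higher non-hematologic toxicity, and its listed exceptions are nausea, emesis and diarrhea only. Three limits follow.
- Section 3.2 requires the event to be considered possibly related to GS-5829.
- Laboratory findings without a clear clinical correlate may be discussed with the medical monitor. A rise then judged not to be a DLT follows the table alone, so there is no conflict.
- Grade 3 or 4 AST/ALT with Grade 2 bilirubin must be called a DLT, but Table 5-1 stops the drug permanently in that case, so restart does not arise.

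**Step 2. Which baselines are in scope?** Inclusion criterion 10b (Section 4.2) limits ALT/AST to 2.5 × ULN without liver metastases, which is Grade 1 or lower on the Table 5-1 bands. With liver metastases, entry up to 5 × ULN is allowed. A Grade 2 baseline narrows or closes the gap, because the text accepts return to baseline. The bilirubin limit is 1.5 × ULN (total or conjugated) with or without liver metastases.

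**Step 3. Compare the thresholds, using the Table 5-1 bands and a baseline of Grade 1 or lower.**

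| Test | Text allows restart at | Table allows restart at | Rules disagree across | Width |
|---|---|---|---|---|
| ALT/AST | ≤3 × ULN | ≤5 × ULN | >3 to 5 × ULN | 5 − 3 = 2 × ULN |
| Bilirubin | ≤1.5 × ULN | ≤3 × ULN | >1.5 to 3 × ULN | 3 − 1.5 = 1.5 × ULN |

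The zone of disagreement is Grade 2 in each case.

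**Step 4. Compare the restart dose.** The text requires at least one level lower. The hepatic row is silent. That is not a contradiction, since the text fills the gap, but a site using the table alone is not told to reduce.

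**Step 5. Look for a precedence rule.** The text's pointer to Table 5-1 does not rank the two. Section 7.1.3 sends the handling of laboratory abnormalities back to Section 5.3.1, where the conflict lies. Section 7.5 sends toxicity questions to the medical monitor. None of these says which rule governs.

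**Step 6. Does the text rule apply only in Day 1 to 28?** This is unclear. Section 3.2 confines a DLT to Day 1 through Day 28. If the reference to that section imports the whole definition, later events follow the table alone: the conflict disappears for them, and the row that then governs names no restart dose. If the reference imports only the type and grade of event, the text rule applies throughout. The preceding sentence, on Grade 4 events, is worded to apply at any time in the study, which might suggest the wider reading but does not settle it.

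**Step 7. Check the 28-day stop.** It is not confined to either route, and resolution is not defined separately for hepatic events. If Grade 2 persists past 28 days, the text reading leads to permanent discontinuation, whereas the table would already have allowed a restart.

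**The case against.** The strongest reply is that the specific rule overrides the general one. Table 5-1 splits non-hematological events into hepatic and non-hepatic blocks, and a separate hepatic block has little purpose unless liver tests are handled differently. A Grade 2 restart threshold also fits the row above it, which continues dosing at Grade 2 with at least weekly tests. Elsewhere the table refines the text: it adds an intermittent schedule as an alternative to a lower dose for non-hepatic Grade 3 events.

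This reading is plausible, but it is not stated anywhere. The text says non-hematologic without exception, and the Grade 2 row concerns events that have not reached Grade 3. Read as a deliberate exception, the hepatic row would still lack its own restart dose.

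The opposite inference is also tempting: that the hepatic row must be a slip. Of the five rows in Table 5-1 that require a hold, four require Grade 1 or lower and state a restart dose or schedule; hepatic Grade 3 is the only one that does neither. The count does not show intent, because a separate hepatic block can be expected to differ.

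The practical safeguards stand. Waiting for Grade 1 or lower satisfies both rules, and the text requires medical monitor discussion before restart.

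**Conclusion.** The section is internally inconsistent and wrong as written, but the point is minor. It holds for an isolated Grade 3 ALT/AST or bilirubin rise, considered possibly related to GS-5829 and judged consistent with a DLT, that does not meet the stopping clause, in a subject with a baseline of Grade 1 or lower. There the two rules give opposite restart decisions across the whole Grade 2 band. Whether this extends beyond Day 28 depends on the unresolved reading in Step 6.

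Three stronger conclusions are not supported.
- **That every Grade 3 liver event is affected.** Events judged not to be DLTs, combined AST/ALT-and-bilirubin events, and many subjects with a Grade 2 baseline fall outside.
- **That the MTD or RP2D evidence is compromised.** An in-scope event in Day 1 to 28 is classed as a DLT before any restart decision, so DLT counts and the dose model do not change.
- **That subjects were harmed or that such events were common.** The documents give no frequency for this trial. The Grade 3 AST DLT described in Section 1.2.3.1 arose at 6 mg in the single-agent escalation of GS-US-350-1599. It shows neither how often the event occurs in this combination nor which restart rule was intended here.

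SAP Section 1 states that all Phase 1b subjects have stopped study drug and had their safety follow-up, so no dosing decision can now change.

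**What to change.** **Default for any reuse of this dosing section.** Amend the hepatic Grade 3 row to match the text: *hold until Grade 1 or lower, or baseline; if this is reached within 28 days, resume at least one dose level lower after medical monitor discussion; otherwise discontinue*. Keep the stopping clause. This also makes the Day 28 question moot for these events, because both sources then give the same rule. It costs one table row; the downside is longer holds or lower doses for some subjects.

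**Alternative, if Grade 2 was intended for liver tests.** Write that exception and its restart dose into the text sentence, and say whether the sentence applies only in the DLT window. Re-exposure at Grade 2 is then accepted openly.

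**For this trial.** Add one sentence to the clinical study report saying which rule was applied to any such event. The data should be in listings the SAP already plans: drug administration (4.2.2.2), AEs leading to dose reduction or interruption (7.1.6.1), DLTs (7.1.7.1) and laboratory results (7.2).

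The conflict between a 3 mg and a 2 mg dose floor in Section 5.3.1 and Table 5-2 is a separate issue and adds no weight here. It does need settling before a one-level reduction can be applied to a subject already on 3 mg.

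### Protocol Section 5.3.1 gives conflicting GS-5829 dose floors (2 mg and 3 mg) and conflicting outcomes for recurrent hematologic toxicity, with no stated precedence

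*Protocol*

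**What the plan says.** All the dosing text is in Protocol Section 5.3.1.

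**Before Table 5-1.** For hematologic recurrence: "If the recurrent toxicity is hematologic a second dose decrease is allowed (lowest dose allowed is 2 mg". The second decrease may lower the daily dose, or change the schedule so that the "total amount of GS-5829 administered over a 28 day period is decreased by at least 25" percent.

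**After Table 5-1.** Two recurrence rules follow.
- The general rule is triggered when a "subject experiences a recurrence of the toxicity after restarting study drug at a lower dose". The consequence is permanent discontinuation of study drug, an end-of-treatment visit and a 30-day safety visit.
- A second rule begins "If a subject develops a recurrence of the same Grade 3 or 4 hematologic or any non-hematologic toxicity". It applies when the investigator considers the event related to GS-5829 and clinically significant at the lower dose. The consequence is permanent discontinuation of all study drugs.

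**Directly above Table 5-2.** "No dose reduction of GS-5829 below 3 mg is allowed".

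**Table 5-2.** The column "Restarting dose level (mg)" gives 9 to 6, 6 to 4, 4 to 3 and 3 to 2 mg. No row is limited to a type of toxicity.

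Section 3.2 sets the Phase 1b starting dose at 4 mg once daily. SAP Section 4.3 counts subjects with important protocol deviations by reason. SAP Section 1 records that the study ended during dose escalation and that all enrolled subjects are off study drug.

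**The concern.** These rules decide whether a subject stays on treatment and at what dose. If two sentences in one section support opposite actions, two sites could manage identical subjects differently and each believe it followed the protocol. Anyone classifying deviations afterwards would have no single standard for judging either action. Both recurrence rules also end the partner drug (exemestane or fulvestrant), so the choice affects more than GS-5829.

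**Working it through.** No power or sample-size formula applies. The check sets the statements side by side and asks whether a subject can reach the point where they diverge.

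**1. Dose floor**

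| Place in Section 5.3.1 | Is 2 mg daily allowed? |
|---|---|
| Text before Table 5-1 | Yes, as the lowest dose, in the sentence on hematologic recurrence |
| Sentence above Table 5-2 | No, and no exception is given |
| Table 5-2, last row | Yes, for any toxicity at 3 mg |

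The second and third entries are adjacent on the page and cannot both be followed.

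**2. Can a subject reach it?** Inputs are the 4 mg starting dose (Section 3.2) and the Table 5-2 steps.
- First reduction: 4 to 3 mg, (4 − 3)/4 = 25% less. The 28-day total falls from 4 × 28 = 112 mg to 3 × 28 = 84 mg.
- Second reduction: 3 to 2 mg, (3 − 2)/3 = 33% less. The 28-day total falls from 84 mg to 2 × 28 = 56 mg.

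The conflict therefore arises at the second single-step reduction. Some steps are worded more loosely (for Grade 4 thrombocytopenia, "the subject may either resume at a dose with is at least one level lower"), so a larger step could reach 2 mg sooner. The point does not depend on that.

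The schedule option is different. From 3 mg daily, at least 25% less means at most 0.75 × 84 = 63 mg per 28 days, for example 3 mg on 21 of 28 days (3 × 21 = 63). That keeps 3 mg on dosing days and need not breach either floor. The floor conflict concerns the daily-dose option only.

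**3. Recurrence.** A second decrease presupposes a first, so the permission addresses the same situation as recurrence after restart at a lower dose. Take a subject reduced from 4 to 3 mg whose hematologic toxicity recurs at 3 mg:

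| Recurrence | Text before Table 5-1 | General rule | Second rule |
|---|---|---|---|
| Same Grade 3 or 4 event, related and clinically significant | Second decrease allowed | Stop | Stop all study drugs |
| Same Grade 3 or 4 event, not judged clinically significant | Second decrease allowed | Stop | Silent |
| Grade 2 event | Second decrease allowed | Stop (no grade limit) | Silent |

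The permission and the general rule disagree in every row. The second rule adds a further stop in the first row only. That row is not marginal: Table 5-1 maintains the dose for thrombocytopenia up to Grade 2, and for neutropenia up to Grade 3 without fever or infection. The hematologic reductions that Table 5-1 directs therefore come from Grade 3 or 4 events.

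**4. Precedence.** Nothing in Section 5.3.1 says which floor governs, or whether the hematologic permission overrides the general rule.

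**The case against.** **The 2 mg floor may be a deliberate hematologic exception to a 3 mg floor.** This is the best reading of the early text, but it does not remove the conflict. The 3 mg sentence carries no exception, and the 3-to-2 mg row is not limited to hematologic events.

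**The recurrence rules may fit together.** The permission can be read as a specific exception to the general rule, with the second rule limiting it: a second decrease is allowed unless the same Grade 3 or 4 event recurs and is related and clinically significant. This reading is coherent, and it stands against anyone who infers that every hematologic recurrence faces an irreconcilable choice. What remains is that the protocol does not state this reading, and the general rule read literally excludes it.

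**The medical monitor resolves unclear cases.** Section 7.5 sends toxicity-management questions to the monitor, and several steps already require that discussion. This gives a route for decisions but does not correct the text or give a later reader one rule.

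**The study is closed.** That is true, and it limits the practical consequence to reporting and any reuse of the text.

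A reader might also infer that the adherence results are distorted. The documents do not support that. Protocol Section 8.6.1 and SAP Section 4.2.2.1 take prescribed reductions into account, and 2 mg is printed in Section 5.3.1. If a 2 mg dose were nevertheless not accepted, the result would depend on an expected dose that the documents do not give. With one cycle each at 4, 3 and 2 mg, all taken, an assumed expected 3 mg in the last cycle gives (4 + 3 + 2)/(4 + 3 + 3) = 90%, while an assumed required stop gives 9/7 = 129%. No adherence effect can be claimed.

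**Conclusion.** The contradiction is real and lies in current, operative text. The floor conflict is direct. The recurrence conflict is a collision between a permission and an unqualified stop rule; a reconciling reading exists but is not stated. For the same subject, re-dosing and stopping each have textual support, so deviation status under SAP Section 4.3 has no single answer.

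The size is modest. Type I error, power and sample size are untouched. Discontinuations, dose modifications and average daily dose can still be tabulated as recorded. A reader might infer that subjects were wrongly dosed or wrongly stopped, but the documents show no such subject. The conclusion rests on the literal wording of Section 5.3.1 and, for reachability, on single Table 5-2 steps from 4 mg. It is worth fixing because the rules govern dosing and stopping and the correction is cheap.

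**What to change.** The sponsor's clinical team should reconcile the text before Table 5-1, the two recurrence rules after it, the 3 mg sentence and Table 5-2. The reconciled text should state the floor, any intended exception, and the precedence between the recurrence rules. Which dose or rule applies is the clinical team's decision, and this review takes no position on it.

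Because all subjects are off drug, the study report should:
- state how these passages were applied;
- identify any subject dosed below 3 mg, or re-dosed after a hematologic recurrence at a lower dose;
- say how those cases were classified for protocol deviations.

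The SAP already plans the source listings: study drug administration (Section 4.2.2.2), and adverse events leading to dose reduction, interruption or discontinuation (Section 7.1.6.1). The cost is a short statement in the report and a text correction before any reuse of the protocol, with no statistical cost.

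Two minor wording points can be tidied in the same pass. The Table 5-2 footnotes number the 4 and 3 mg levels differently from Section 3.2, and the hepatic Grade 3 row of Table 5-1 gives no restart dose. Neither bears on the conclusion.
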